5.1.2. Period 2: Double-Blind, Placebo-Controlled Treatment

Patient will be randomized at a 1:1:1 ratio into 1 of the 3 treatment groups (placebo QD, baricitinib 2-mg QD, or baricitinib 4-mg QD). Investigational product will be administered daily for 16 weeks (treatment period Visits 2 through 8; Section 7). All patients will be required to use emollients daily. Daily diaries will continue to be utilized throughout the treatment period. Download of this data will be required at study visits. TCS will be dispensed at V2 and used on affected areas as described in section 7.7.2. Topical calcineurin inhibitors (TCNIs) is also allowed, but TCNI use should be limited to problem areas (e.g. face and skin folds). The use of higher potency TCS, ~~erisaborole~~, and systemic therapies for the treatment of AD are not allowed, except as part of rescue therapy for patients not responding to treatment. Details of background topical therapy, as well as rescue therapy and rescue criteria are included in Section 7.7. Assessments of disease severity will be performed by the investigator at all study visits including unscheduled and early termination visits (ETVs).

5.4. Scientific Rationale for Study Design

This study will enroll moderate to severe AD patients with a history of inadequate response ~~or intolerance~~ to existing topical therapies for whom a systemic treatment such as baricitinib may therefore be appropriate.

6.1. Inclusion Criteria

Type of Patient and Disease Characteristics

- [6] agree to discontinue use of the following excluded medications/treatments for at least 4 weeks prior to randomization (Visit 2) and throughout the study:
- oral systemic corticosteroids ~~and leukotriene inhibitors~~
 - systemic immunomodulators, including, but not limited to, cyclosporine, methotrexate, mycophenolate mofetil, and azathioprine
 - any other systemic therapy used to treat AD or symptoms of AD (approved or off-label use)

7.7.4. Rescue Therapy

Rescue with High- and Ultra-High-Potency TCS

High- or ultra-high-potency TCS may be used once daily for up to 14 consecutive days or less, or based on the maximum duration recommended in the prescribing information.

8.1.2. ***Permanent Discontinuation from Investigational Product***

Investigational product should be permanently discontinued if the patient requests to discontinue investigational product.

Discontinuation of the investigational product for abnormal liver tests should be considered by the investigator when a patient meets 1 of the following conditions after consultation with the Lilly-designated medical monitor:

- ALT or AST >8x ULN
- ALT or AST >5x ULN for more than 2 weeks
- ALT or AST >3x ULN and total bilirubin level (TBL) >2x ULN or international normalized ratio (INR) >1.5
- ALT or AST >3x ULN with the appearance of fatigue, nausea, vomiting, right upper-quadrant pain or tenderness, fever, and/or rash, ~~and/or eosinophilia (>5%)~~
- ALP >3x ULN
- ALP >2.5x ULN and TBL >2x ULN
- ALP >2.5x ULN with the appearance of fatigue, nausea, vomiting, right quadrant pain or tenderness, fever, and/or rash, ~~and/or eosinophilia (>5%)~~

NOTE: Patients who are discontinued from investigational product due to a hepatic event or liver test abnormality should have additional hepatic safety data collected via the hepatic safety eCRF.

### 3. Revision History

Statistical Analysis Plan (SAP) Version 1 is based on Protocol I4V-MC-JAIY(a). Statistical Analysis Plan Version 2 was approved prior to unblinding. A summary of changes between Version 1 and Version 2 are as follows:

Section	Summary of Changes
4.3. Exploratory objectives	
 
• Updated the time frame for the objective of frequency of patient-reported “no itch” and “no pain” by starting from Week 0.
 
• Added new exploratory analyses on Hospital Anxiety Depression (HADS), Dermatology Life Quality Index (DLQI), Atopic Dermatitis Sleep Scale (ADSS), and Patient-Oriented Eczema Measure (POEM).
 
• Added new exploratory analyses on early responders.
 

6.11.1. Background TCS	
 
• Updated the weight of dispensed topical corticosteroids (TCS) tube to align with JABL SAP.
 

6.2.2. Definition on Baseline and Postbaseline Measures	
 
• Updated the derivations of itch weekly scores.
 

6.2.3. Analysis Methods	
 
• Updated the structures of covariance matrix in mixed model repeated measures (MMRM) model.
 

6.6. Multiple Comparisons	
 
• Updated the graphical testing procedure.
 

6.16 Subgroup Analysis	
 
• Added subgroup analyses for East Asia vs. other.
 

Table 6.6	
 
• Updated the endpoints on the number days of itch-free and pain-free days.
 

Table 6.7	
 
• Updated analyses on the number of itch-free and pain-free days.
 
• Change the type of analysis of covariance (ANCOVA) (modified last observation carried forward [mLOCF]) analyses on PROMIS from “exploratory analyses” to “sensitivity analyses.”
 

## 4. Study Objectives

### 4.1. Primary Objective

The primary objective of this study is to test the hypothesis that baricitinib 4 mg once daily (QD) plus topical corticosteroids (TCS) or baricitinib 2 mg QD plus TCS is superior to placebo plus TCS in the treatment of patients with moderate to severe atopic dermatitis (AD), as assessed by the proportion of patients achieving the validated Investigator's Global Assessment for AD (vIGA-AD, referred to throughout the SAP as IGA) of 0 or 1 with a  $\geq 2$ -point improvement at Week 16.

In particular, the associated estimand for this objective is to measure the effect of therapy with baricitinib as assessed by the proportion of patients with a response of IGA 0 or 1 at Week 16 assuming treatment response disappears after patients are rescued or discontinued from the study or treatment. See Sections 6.4.1 and 6.12.1 on how this estimand handles outcomes after the occurrence of any intercurrent event through nonresponder imputation (NRI).

### 4.2. Secondary Objectives

#### 4.2.1. Key Secondary Objectives

These are prespecified objectives that will be adjusted for multiplicity.

Objectives	Endpoints
To compare the efficacy of baricitinib 2 mg QD + TCS or baricitinib 4 mg QD + TCS to placebo + TCS in AD during the 16-week double-blind placebo-controlled treatment period as measured by improvement in signs and symptoms of AD.	
 
Proportion of patients achieving EASI75 at 16 weeks
 
Proportion of patients achieving EASI90 at 16 weeks
 
Percent change from baseline in EASI score at 16 weeks
 
Proportion of patients achieving SCORAD75 at 16 weeks
 

To compare the efficacy of baricitinib 2 mg QD + TCS or baricitinib 4 mg QD + TCS to placebo + TCS in AD during the 16-week double-blind placebo-controlled treatment period as assessed by patient-reported outcome measures.	
 
Proportion of patients achieving a 4-point improvement from baseline in Itch NRS at 2 days, 1 week, 2 weeks, 4 weeks, and 16 weeks
 
Mean change from baseline in the score of Item 2 of the ADSS at 1 week and 16 weeks
 
Mean change from baseline in Skin Pain NRS at 16 weeks
 

#### 4.2.2. Other Secondary Objectives

These are prespecified objectives that will not be adjusted for multiplicity.

Objectives	Endpoints
To test the hypothesis that baricitinib 2 mg QD + TCS or baricitinib 4 mg QD + TCS is superior to placebo + TCS in the treatment of patients with moderate to severe AD.	
 
• Proportion of patients achieving IGA of 0 or 1 with a <math>\geq 2</math>-point improvement at Week 4
 

To compare the efficacy of baricitinib 2 mg QD + TCS or baricitinib 4 mg QD + TCS to placebo + TCS in AD during the 16-week double-blind placebo-controlled period as measured by signs and symptoms of AD.	
 
• Proportion of patients achieving EASI50 at 16 weeks
 
• Proportion of patients achieving IGA of 0 at 16 weeks
 
• Mean change from baseline in SCORAD at 16 weeks
 
• Proportion of patients achieving SCORAD90 at 16 weeks
 
• Mean change from baseline in BSA affected at 16 weeks
 
• Proportion of patients developing skin infections requiring antibiotic treatment by Week 16
 
• Mean gram quantity of background TCS used over 16 weeks (tube weights)
 

To compare the efficacy of baricitinib 2 mg QD + TCS or baricitinib 4 mg QD + TCS to placebo + TCS in AD during the 16-week, double-blind, placebo-controlled treatment period as assessed by patient-reported outcome/QoL measures.	
 
• Percent change from baseline in Itch NRS at 2 days, 1 week, 4 weeks, and 16 weeks
 
• Mean change from baseline in Itch NRS at 2 days, 1 week, 4 weeks and 16 weeks
 
• Proportion of patients achieving a 4-point improvement from baseline in Skin Pain NRS at 16 weeks
 
• Mean change from baseline in the total score of the POEM at 16 weeks
 
• Mean change in the PGI-S-AD scores at 16 weeks
 
• Mean change from baseline in HADS at 16 weeks
 
• Mean change in the DLQI scores at 16 weeks
 
• Mean change in the WPAI scores at 16 weeks
 
• Mean change in the EQ-5D-5L scores at 16 weeks
 
• Mean number of days without use of background TCS over 16 weeks
 

### 4.3. Exploratory Objectives

The exploratory objectives of this study are the following:

Objectives/Endpoints

 
• Frequency of patient-reported “no itch” (Itch NRS score = 0) days from daily diaries from Week 0 to Week 16
 
• Frequency of patient-reported “no pain” (Skin Pain NRS score = 0) days from daily diaries from Week 0 to Week 16
 
• Mean change from baseline in PIQ – Itch Interference score
 
• Mean change from baseline in PIQ – Activity and Clothing score
 
• Mean change from baseline in PIQ – Mood and Sleep score
 
• Mean change from baseline in PIQ – Scratching Behavior score
 
• Mean change from baseline in PROMIS – Sleep-Related Impairment score
 
• Mean change from baseline in Neuro-QoL – Cognitive Function score
 
• Patient Benefit Index score at 16 weeks – global score plus the following subscales: 
 
○ Reducing social impairments
 
○ Reducing psychological impairments
 
○ Reducing impairments due to therapy
 
○ Reducing physical impairments
 
○ Having confidence in healing
 
 
 
• Proportion of patients achieving PBI global score <math>\geq 1</math> at 16 weeks
 
• Mean change from baseline in the score of Item 1 of the ADSS at 1 week and 16 weeks
 
• Proportion of patients achieving a <math>\geq 1</math>-point improvement in the score of Item 1 of the ADSS for those with baseline Item 1 score <math>\geq 1</math>
 
• Proportion of patients achieving a <math>\geq 1</math>-point improvement in the score of Item 2 of the ADSS for those with baseline Item 2 score <math>\geq 1</math>
 
• Proportion of patients achieving a <math>\geq 2</math>-point improvement in the score of Item 2 of the ADSS for those with baseline Item 2 score <math>\geq 2</math>
 
• Mean change from baseline in the score of Item 3 of the ADSS at 1 week and 16 weeks
 
• Proportion of patients achieving a <math>\geq 1</math>-point improvement in the score of Item 3 of the ADSS for those with baseline Item 3 score <math>\geq 1</math>
 
• To evaluate changes from baseline in immunoglobulin E levels during the study
 
• To evaluate changes from baseline in eosinophil levels during the study
 
• To assess time to 4-point Itch NRS improvement during the first 14 days after initiation of treatment
 
• To assess time to 4-point improvement in Skin Pain during the first 14 days after the initiation of treatment
 
• Proportion of patients achieving a <math>\geq 4</math>-point improvement in DLQI total score for those with baseline DLQI total score <math>\geq 4</math>
 
• Proportion of patients achieving DLQI total score 0 or 1
 
• Proportion of patients achieving a <math>\geq 4</math>-point improvement in POEM total score for those with baseline total score <math>\geq 4</math>
 
• Proportion of patients achieving HADS Anxiety Score <math>< 8</math> for those with baseline HADS Anxiety Score <math>\geq 8</math>
 
• Proportion of patients achieving HADS Depression Score <math>< 8</math> for those with baseline HADS Depression Score <math>\geq 8</math>
 
• Proportion of patients achieving improvement with HADS Anxiety Score or HADS Depression Score <math>< 8</math> for those with baseline HADS Anxiety Score <math>\geq 8</math> or HADS Depression Score <math>\geq 8</math>
 
• Mean change from baseline in HADS subscale scores
 


- Proportion of patients achieving  $\geq 4$ -point improvement in Itch NRS or IGA $\leq 1$  at Week 16 for those with  $\geq 3$ -point improvement in Itch NRS or IGA $\leq 2$  at Week 4
- Proportion of patients achieving  $\geq 4$ -point improvement in Itch NRS or IGA $\leq 1$  at any time between Week 8 and Week 16 for those with  $\geq 3$ -point improvement in Itch NRS or IGA $\leq 2$  at Week 4
- Proportion of patients achieving  $[\geq 4$ -point improvement in Itch NRS and IGA $\leq 2]$  or [IGA $\leq 1]$  at Week 16 for those with  $\geq 3$ -point improvement in Itch NRS or IGA $\leq 2$  at Week 4
- Proportion of patients achieving  $[\geq 4$ -point improvement in Itch NRS and IGA $\leq 2]$  or [IGA $\leq 1]$  at any time between Week 8 and Week 16 for those with  $\geq 3$ -point improvement in Itch NRS or IGA $\leq 2$  at Week 4

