### **6.4.1. Nonresponder Imputation**

A nonresponder imputation (NRI) method imputes missing values as non-responses and can be justified based on the composite strategy for handling intercurrent events (ICH E9 R1). This imputation procedure assumes the effects of treatments disappear after the occurrence of an intercurrent event defined by the associated censoring rule.

All categorical endpoints will utilize the NRI method after applying the primary censoring rule to patients who permanently discontinued study drug or were rescued (described in Section 6.4). Additionally, all primary and key secondary categorical endpoints will utilize NRI after applying the secondary censoring rule as sensitivity analyses. For analyses which utilize either of the censoring methods, randomized patients without at least 1 post-baseline observation will be defined as nonresponders for all visits.

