		Change from baseline in POEM score	Change from baseline: observed POEM score – baseline POEM score	Missing if baseline or observed value is missing.
		4-point improvement in POEM score in subgroup of patients with baseline $\geq 4$	Change from baseline $\leq -4$ and baseline $\geq 4$	Missing if baseline is missing or $< 4$ or observed value is missing.

Measure	Description	Variable	Derivation / Comment	Imputation Approach if Missing Components
Patient Global Impression of Severity–Atopic Dermatitis (PGI-S-AD)	The Patient Global Impression of Severity–Atopic Dermatitis (PGI-S-AD) is a single-item question asking the patient how they would rate their overall AD symptoms over the past 24 hours. The 5 categories of responses range from “no symptoms” to “severe.”	PGI-S-AD score	Single item. Range 1 to 5. Refer to Section 6.2.2 on how to derive the visit score.	Refer to Section 6.2.2 on how to derive the visit score.
		Change from baseline in PGI-S-AD	Change from baseline: observed PGI-S-AD score – baseline PGI-S-AD score	Missing if baseline or observed value is missing.
Hospital Anxiety Depression Scale (HADS)	The Hospital Anxiety Depression Scale (HADS) is a 14-item self-assessment scale that determines the levels of anxiety and depression that a patient is experiencing over the past week. The HADS utilizes a 4-point Likert scale (e.g., 0 to 3) for each question and is intended for ages 12 to 65 years (Zigmond and Snaith 1983; White et al. 1999). Scores for each domain (anxiety and depression) can range from 0 to 21, with higher scores indicating greater anxiety or depression (Zigmond and Snaith 1983; Snaith 2003).	HADS score for anxiety and depression domains	Anxiety domain score is sum of the seven anxiety questions, range 0 to 21; Depression domain score is sum of the seven depression questions, range 0 to 21.	N/A – partial assessments cannot be saved.
		Change from baseline in HADS total score, anxiety and depression domain	Change from baseline: observed HADS domain score – baseline HADS domain score	Missing if baseline or observed value is missing.

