	Proportion of patients achieving a 4- point improvement in Skin Pain NRS in subgroup of patients with baseline Skin Pain NRS $\geq 4$	Logistic regression using NRI	ITT	Bari 4 mg or Bari 2 mg vs PBO; Week 1,..., 16	Other Secondary Analysis
Atopic Dermatitis Sleep Scale (ADSS)	
 
ADSS item scores
 
Change from baseline in ADSS item scores
 
	MMRM	ITT	Bari 4 mg or Bari 2 mg vs PBO; Week 1,..., 16	Key Secondary Analysis at Week 1 and 16
			PPS	Bari 4 mg or Bari 2 mg vs PBO; Week 16	Sensitivity analysis
		ANCOVA using mLOCF	ITT	Bari 4 mg or Bari 2 mg vs PBO; Week 1,..., 16	Sensitivity Analysis
		pMI	ITT	Bari 4 mg or Bari 2 mg vs PBO; Week 16	Sensitivity analysis
Patient-Oriented Eczema Measure (POEM)	
 
POEM score
 
Change from baseline in POEM score
 
	MMRM	ITT	Bari 4 mg or Bari 2 mg vs PBO; at each post-baseline visit	Secondary Analysis
			ANCOVA using mLOCF	ITT	Bari 4 mg or Bari 2 mg vs PBO; Week 16
	Proportion of patients achieving a 4- point improvement in subgroup of patients with baseline POEM $\geq 4$	Logistic regression using NRI	ITT	Bari 4 mg or Bari 2 mg vs PBO; at each post-baseline visit	Secondary Analysis
Patient Global Impression of Severity–Atopic Dermatitis (PGI-S- AD)	
 
PGI-S-AD score
 
Change from baseline in PGI-S-AD score
 
	MMRM	ITT	Bari 4 mg or Bari 2 mg vs PBO; at each post-baseline visit	Secondary Analysis
			ANCOVA using mLOCF	ITT	Bari 4 mg or Bari 2 mg vs PBO; Week 16

Measure	Variable	Analysis Method (Section 6.2.3)	Population (Section 6.2.1)	Comparison/Time Point	Analysis Type
Hospital Anxiety Depression Scale (HADS)	
 
HADS domain scores
 
Change from baseline in HADS domain
 
	MMRM	ITT	Bari 4 mg or Bari 2 mg vs PBO; Week 2, 4, 8, 16	Secondary Analysis
		ANCOVA using mLOCF	ITT	Bari 4 mg or Bari 2 mg vs PBO; Week 16	Sensitivity Analysis
Dermatology Life Quality Index (DLQI)	
 
DLQI total score
 
Change from baseline in DLQI
 
Observed and change from baseline in domain scores 
 
-Symptoms and feelings
 
-Daily activities
 
-Leisure
 
-Work and school
 
-Personal relationships
 
-Treatment
 
 
 
	MMRM	ITT	Bari 4 mg or Bari 2 mg vs PBO; Week 16	Secondary Analysis

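### The combined exploratory HADS responder endpoint can count a patient with one raised subscale as improved when that subscale has not improved

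*SAP*

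**What the plan says.** SAP Section 4.3 has three HADS threshold endpoints. The first two are single-subscale. The Anxiety one is the "Proportion of patients achieving HADS Anxiety Score" below 8, "for those with baseline HADS Anxiety Score" at or above 8, and the Depression one has the same form. The third is combined: "Proportion of patients achieving improvement with HADS Anxiety Score or HADS Depression Score" below 8, among patients with baseline Anxiety or baseline Depression at or above 8. Both the entry condition and the response condition are joined by *or*.

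The subscales are scored separately. Table JAIY.6.6 states "Anxiety domain score is sum of the seven anxiety questions, range 0 to 21; Depression domain score is sum of the seven depression questions", each from 0 to 21 with higher scores worse. Its HADS rows cover the "HADS score for anxiety and depression domains" and the change from baseline, and give no responder variable. Table JAIY.6.7 lists the domain scores and "Change from baseline in HADS domain", analysed by MMRM and by ANCOVA with mLOCF, and no HADS responder analysis. On missing data, SAP Section 6.4.1 says "All categorical endpoints will utilize the NRI method after applying the primary censoring rule".

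**The concern.** In the two single-subscale endpoints the subscale that admits the patient is the one that must normalise. The combined endpoint breaks that link. A patient with Anxiety 14 and Depression 4 at baseline enters through Anxiety and already satisfies the response threshold through Depression. The reported proportion would then mix patients whose raised score came down with patients who had nothing to achieve. A reader would take it as the proportion whose anxiety or depression resolved.

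**Working it through.** The plan gives no figure for this endpoint, so the check is on the rule itself.

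**Inputs.** Each subscale runs from 0 to 21 (Table JAIY.6.6). Entry is A ≥ 8 or D ≥ 8, and the response threshold is A < 8 or D < 8 (Section 4.3). Nonresponder imputation (NRI) applies after the primary censoring rule (Sections 6.4 and 6.4.1).

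**Score pairs.** A subscale has 8 values below 8 (0 to 7) and 14 at or above 8 (8 to 21).
- All pairs: 22 × 22 = 484. Neither raised: 8 × 8 = 64. Eligible: 484 − 64 = 420.
- Exactly one raised: 2 × 14 × 8 = 224. Both raised: 14 × 14 = 196. Sum: 420.
- With no change from baseline, all 224 one-raised pairs satisfy A < 8 or D < 8, and none of the 196 both-raised pairs do. 224/420 = 53.3% of score pairs.
- For the single-subscale endpoints, none of the 14 raised values passes with no change.

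**A worsening patient.** Going from A = 12, D = 5 to A = 21, D = 7 passes the threshold through D = 7, although both scores rose.

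**Direction of the rates.** Anyone with both subscales below 8 also has at least one below 8. Likewise, anyone whose every raised subscale has fallen below 8 has at least one below 8. Responders under either resolution rule are therefore a subset of responders under the threshold as written. In each arm the written rule cannot give a lower rate, and it gives a higher one as soon as one such patient is observed and uncensored.

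**Size.** Let s be the one-raised share of the denominator. Let c be the share of one-raised patients in an arm who are nonresponders (rescued, off study drug, missing, or with both subscales at 8 or more at that visit). Let q be the response rate in both-raised patients. Then

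rate = s(1 − c) + (1 − s)q

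difference = s(c placebo − c active) + (1 − s)(q active − q placebo).

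The documents give none of s, c or q. For illustration only, assume a resolution rate of 30% on placebo and 45% on baricitinib, with the two subscales moving together in both-raised patients so that q takes these values. The resolution difference is then 15 points.

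| s | c = 0 in both arms | c = 30% placebo, 15% active |
|---|---|---|
| 30% | 51.0 vs 61.5 (10.5 points) | 42.0 vs 57.0 (15 points) |
| 50% | 65.0 vs 72.5 (7.5 points) | 50.0 vs 65.0 (15 points) |
| 70% | 79.0 vs 83.5 (4.5 points) | 58.0 vs 73.0 (15 points) |

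For example, at s = 50% with c = 0, placebo is 0.5 × 100 + 0.5 × 30 = 65. With c = 30%, it is 0.5 × 70 + 0.5 × 30 = 50. Both columns exceed 30% and 45%. The difference shrinks in the first column and not in the second, where the one-raised group reports an arm difference in rescue and dropout rather than in HADS.

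**The case against.** The best counter-argument is the word *improvement*. It appears in the combined endpoint and not in the two single-subscale ones, and an unchanged patient has not improved in ordinary language. The authors may have meant simply to pool the two preceding endpoints. That stands as a statement of possible intent. It does not settle the rule, because the word is never defined for HADS and no derivation row gives it content. Even if it meant any fall in score, a move from Anxiety 14 to 13 with Depression unchanged at 4 would qualify. Only a reading in which the raised subscale itself must fall below 8 removes the problem, and the plan does not state it.

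Two further points stand. First, a reader might infer that every one-raised patient is a responder at every visit. The documents do not support that: rescue, permanent discontinuation of study drug or a missing score makes the patient a nonresponder, and so does a rise of the unraised subscale to 8 or more while the other stays raised. Second, a reader might infer that the treatment difference shrinks by exactly the factor 1 − s. That requires no arm difference among one-raised patients, which NRI does not guarantee. It also requires both-raised patients to respond at the resolution rate, although they need only one subscale to normalise.

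The reach is also small. The endpoint is exploratory and carries no multiplicity adjustment. HADS is also covered by the two sound single-subscale endpoints and by mean change. SAP Section 6.2 does not promise every display in the study report.

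**Conclusion.** The point holds as a defect in one exploratory endpoint. As written, the only operational criterion is met at baseline by every patient with exactly one raised subscale (224 of 420 eligible score pairs). Such a patient is counted as a responder if observed and uncensored with the unraised subscale below 8, whatever happens to the raised one. That the rates are inflated in all arms follows from the rule alone. Dilution of the treatment difference is probable, but its size is unknown: it depends on the one-raised share, which the documents do not give, and on how rescue and dropout differ by arm. The 53.3% must not be read as a share of patients, and the table above is not a forecast. No primary, key secondary, safety or sample-size conclusion depends on this endpoint.

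**What to change.** In SAP Section 4.3, keep the entry condition and change the response to Anxiety < 8 **and** Depression < 8 after baseline, which is the exact complement of entry. The alternative is to require every subscale at 8 or more at baseline to be below 8. Under either rule 0 of the 420 eligible pairs respond with no change. The two differ in one respect: if Anxiety goes from 12 to 6 while Depression goes from 7 to 8, the patient fails the first rule and passes the second. The sponsor should choose one and say so.

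Add the chosen derivation to the HADS rows of Table JAIY.6.6. Add a row for logistic regression with NRI to Table JAIY.6.7, naming the visits and the baseline covariate: Section 6.2.3 calls for a baseline value in the model, and no single combined HADS value is derived.

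The cost is a short change in Section 4.3 and two table rows, with no new data. Reported response rates will be lower. Under the *and* rule a patient whose unraised subscale rises to 8 or more becomes a nonresponder.
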